#### Treatment Phase:

- Participants will begin study therapy within 14 days of completing screening.
- Adverse event assessments will be documented at each visit throughout the study.
- All of the laboratory tests and vital signs will be collected prior to study drug dosing at the time points specified in the Study Calendar (Table 10).
- All of a participant's study scans (screening scan(s), active-treatment scans, and off-treatment scan) will be reviewed for volumetric analysis (*as well as follow-up scans for participants in active follow-up*). See Section 10.2.
- Study drug dosing may be delayed for toxicity. See Section 6.1.
- Treated subjects will be evaluated for response by the investigator according to the iRANO criteria (Section 11.2) every 8 weeks  $\pm$  1 week until disease progression or treatment discontinuation, whichever occurs later.
- Treated subjects will be evaluated for neurologic functioning by the investigator and according to the NANO scale (Section 11.6). Assessments will be performed at baseline scan and every 8 weeks ( $\pm$  1 week) thereafter, at the time of imaging response assessment until disease progression or treatment discontinuation, whichever occurs later.

This phase ends when the subject experiences a confirmed tumor progression, unacceptable toxicity, or other discontinuation criteria, whichever occurs first. For a complete list of reasons for taking a participant off protocol therapy, see Section 5.10.

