#### Active Follow-Up:

- Participants who discontinue treatment for reasons other than tumor progression will continue to have tumor assessments at intervals determined by the treating investigator until unequivocal disease progression, initiation of a new therapy, or withdrawal of consent. All radiologically determined disease progression must be confirmed by an additional confirmatory MRI scan up to 12 weeks following the initial assessment of

CONFIDENTIAL

This document is confidential. Do not disclose or use except as authorized.

radiological progression. Investigators may obtain additional follow-up MRI scans prior to 12 weeks as medically appropriate.

Long Term Follow-Up:

- After completion of the first follow-up visits, subjects will be followed every 3 months (+/- 1 month) for survival, post-study-therapy therapies, and future relapses.

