- a. All screening procedures to be performed within 14 days prior to start of study treatment, except informed consent (which may occur up to 28 days prior to start of study treatment).
- b. C1D1 and Day 1 of subsequent cycles:
  - For C1D1 only, screening assessments may serve as day 1 assessments, except pregnancy test (within 72 hrs of drug) and vital signs & oxygen saturation (within 3 days prior to drug), except in the event that there are any indications that the participant's condition is deteriorating for which laboratory evaluations should be repeated within 48 hrs prior to initiation
  - For all subsequent cycles, required assessments should be performed within 3 days prior to dose.
- c. *Intentionally blank*
- d. End of Tx: End of treatment assessments to be performed within 7 days after last day drug administration or within 7 days after decision to end treatment. Assessments may continue for ongoing reportable adverse events.
- e. 30-Day Post Drug: A contact/visit is to be performed at 30 days (+/-7 days) after date of last study drug administration. This may be performed via documented phone conversation with a study nurse or clinician or a clinic visit. All participants will be followed until resolution or stabilization of any serious or reportable adverse events occurring during treatment or starting within 30 days of last study drug.
- f. Active Follow-Up: Applies only to those pts who did not progress while on study therapy (including pts who start subsequent anti-cancer therapy), until documented disease progression or pt comes off study for some other reason. Participants will be followed every 3 months (+/- 1 month). See footnote x for scan schedule during Active Follow-Up. Once progression is confirmed, participants will enter long-term follow-up.
- g. Participants enter Long-Term Follow-Up after coming off active treatment for disease progression or after completion of Active Follow-Up: Participants will be followed every 3 months (+/- 1 month) via contact or medical record review until death for post-treatment therapies, reason for stopping those therapies, and survival.

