  - On-study imaging should be performed every 8 weeks (+/- 1 week) and should follow calendar days (i.e. should not be adjusted for delays in cycle starts or extension of Nivolumab cycles).
  - Active Follow-Up: Applies only to those pts who did not progress while on study therapy (including pts who start subsequent anti-cancer therapy), until documented disease progression or pt comes off study for some other reason. MRI schedule & response assessments will be determined by treating investigator.
- y. Response Assessment – Per iRANO criteria (section 11);
- z. The NANO scale (Section 11.6) will be completed by study physician prior to Cycle 1 Day 1 dose, and then with each MRI (but must be completed before MRI scan results are reviewed with the subject) using the scorecard provided in Appendix F.
- aa. 240 mg Nivolumab administered every 2 weeks (-2/+5 days)
  - There must be a minimum of 12 days (11 non-dosing days) between administrations
  - The start and stop time of the nivolumab infusion administration should be documented.
  - Participants who have received active study therapy for >/= 6 months will be allowed the option to adjust their Nivolumab dosing schedule from 240 mg once every 2 weeks (-2/+5 days) to 480 mg once every 4 weeks (+/- 1 week).
- bb. Blood (serum) for soluble biomarkers: to be collected & submitted per section 9.1 and Appendix E, prior to C1D1 study treatment and prior to C5D1 study treatment (or at off-treatment for any participant who comes off-treatment prior to C5D1).
- cc. Peripheral Blood Mononuclear Cells (PBMCs): to be collected & submitted per section 9.1 and Appendix E, prior to C1D1 study treatment and prior to C5D1 study treatment.
- dd. Submission of archival tumor tissue: submission of available tissue from most recent pre-registration biopsy/surgery (per section 9.1 and Appendix E) to be submitted within 60 days of registration, if feasible.
- ee. Submission of tumor sample at the time of progression or suspected progression: submission of available tissue from tumor sample at the time of progression or suspected progression (per section 9 and Appendix E) within 60 days of resection, biopsy, if feasible. This is an optional submission.
- ff. Post-end-of-treatment oncology therapies: start/stop dates, names of treatment regimens and reason for stopping should be collected.
- gg. Survival: date of death and reason should be collected for overall survival purposes, when applicable.

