## **11. MEASUREMENT OF EFFECT**

Tumor response will be assessed by MRI (or CT, if MRI contraindicated) every 8 weeks (+/- 1 week) for patients treated on this study using iRANO criteria as outlined below. Clinicians may repeat response assessment more frequently as clinically indicated.

Local radiologic assessment of tumor measurements will be used during the study for clinical management and investigator-assessed disease progression. Cases of suspected radiologic disease progression will be confirmed by an MRI (or CT, as applicable) performed approximately 12 weeks after the initial radiological assessment of progression.

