## 11.2 Efficacy Assessments (Response/Progression Categories)

The primary efficacy measure of the study is progression-free survival at 6 months (PFS-6). PFS-6 is defined as the proportion of participants in the analysis population who remain progression-free for at least six months following initiation of study therapy. OS will be followed continuously while subjects are on study drug and every 3 months via in-person or phone contact during the survival follow-up phase of the study (see Section 5.2).

Investigator-assessed tumor response will be based upon iRANO criteria. Tumor assessments will be performed at baseline and then every 8 weeks (+/- 1 week) thereafter. Radiologic response will be assessed by comparing the pretreatment baseline and on-treatment MRI scans. Radiologic progression will be determined by using the smallest tumor measurement at either the pretreatment baseline or after initiation of study medication. Table 11.2-1 describes the radiologic and clinical criteria that will be used for determining tumor response.

Table 11.2-1 iRANO Criteria for Response Assessment Incorporating MRI and Clinical Factors	
Response	Criteria
Complete Response	
Requires all of the following:
 
 
• Complete disappearance of all enhancing measurable and non-measurable disease sustained for at least 4 weeks;
 
• No new lesions;
 
• Stable or improved non-enhancing (T2/FLAIR) lesions;
 
• Patients must be off corticosteroids (or on physiologic replacement doses only);
 
• And stable or improved clinically.
 
 
Note: Patients with non-measurable disease only cannot have a complete response; the best response possible is stable disease.

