#### 14.1.2.2 Secondary Endpoints

Secondary endpoints for this study include median PFS, median overall survival (OS), objective radiologic response rate (ORR) and assessment of safety/toxicity.

PFS is defined as the time from initiation of study therapy to the date of the first documented tumor progression or death due to any cause. Participants who die without a reported prior progression will be considered to have progressed on the date of death. Participants who did not have disease progression or die will be censored at the date of last tumor assessment. Participants who did not have any on study tumor assessment and did not die will be censored at date of last follow-up. Participants who started any subsequent anti-cancer therapy without a prior reported progression will be censored at the last tumor assessment prior to initiation of the subsequent anti-cancer therapy, which excludes the surgical resection for differentiating radiology progression from pseudoprogression. Participants who had surgical resection for differentiating radiologic progression from pseudoprogression and tumor pathology confirms disease progression will be defined as progressive as of the date of radiographic progression that led to surgery. PFS will be determined by investigator reported response based on iRANO criteria (Section 6.4). Tumor assessment will occur every 8 weeks (+/- 1 week) until disease progression is documented. Subjects with non-measurable disease at baseline will be considered to have progressed if there is an appearance of new lesions consistent with tumor, any unequivocal increase in baseline enhancing disease, the unequivocal appearance of new tumor growth or re-growth at prior surgical sites, or clinical deterioration.

ORR is defined as the number of subjects whose best overall response (BOR) is confirmed CR or PR divided by response evaluable subjects (Section 11.1.2). The best overall response (BOR) is determined once all the data for the subject is known. BOR is defined as the best

CONFIDENTIAL

This document is confidential. Do not disclose or use except as authorized.

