response designation, as determined by investigators, recorded between the date of study therapy initiation and the date of objectively documented progression per iRANO criteria (Section 11.5), the date of subsequent therapy, or date of surgical resection, whichever occurs first. For subjects without documented progression, subsequent therapy, or surgical resection, all available response designations will contribute to the BOR assessments. BOR will be determined by investigator reported response based on iRANO criteria.

Tumor assessments will occur every 8 weeks thereafter until disease progression is documented or the end of the study. For purposes of this protocol analysis, if a response evaluable subject discontinues from the study or receives a subsequent therapy prior to the 8-week tumor assessment, this subject will be counted in the denominator as a non-responder.

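### After an early stop without progression, the calendar leaves scan timing to the investigator, while Sections 5.3 (Treatment Phase) and 14.1.2.2 carry 8-weekly assessment to progression

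*Combined protocol and SAP*

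**What the plan says.** Two places leave scan timing after an early stop to the investigator. In Section 5.3 (Active Follow-Up), patients who stop for reasons other than progression "will continue to have tumor assessments at intervals determined by the treating investigator". Footnote x of the study calendars says "MRI schedule & response assessments will be determined by treating investigator". Footnote f sets three-monthly follow-up (+/- 1 month) for these patients and defers on imaging: "See footnote x for scan schedule during Active Follow-Up".

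Three places carry the 8-weekly schedule to progression:
- Section 5.3 (Treatment Phase): "until disease progression or treatment discontinuation, whichever occurs later".
- Section 14.1.2.2, under PFS: "Tumor assessment will occur every 8 weeks (+/- 1 week) until disease progression is documented".
- Section 14.1.2.2, under response: "Tumor assessments will occur every 8 weeks thereafter until disease progression is documented or the end of the study".

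Two more set the interval without an end point: Section 11 ("every 8 weeks (+/- 1 week) for patients treated on this study using iRANO criteria") and Section 11.2 ("Tumor assessments will be performed at baseline and then every 8 weeks (+/- 1 week) thereafter").

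The primary endpoint is the proportion of the analysis population progression-free for at least six months, by investigator assessment (Section 14.1.2.1). Success is at least 10 patients of 25 (Section 14.1.4). A cohort stops at interim with 2 or fewer of its first 10 evaluable patients progression-free (Section 14.1.5.1).

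**The concern.** PFS-6 is an open-label count in which one patient is 4 percentage points of 25. Progression is dated when first documented (Section 14.1.2.2), so what is counted depends on when scans are done. If an off-treatment patient is scanned less often before month 6, two things can happen. Radiographic progression before month 6 may go unseen and the patient be counted as a success. Or there may be no scan that settles six-month status. The first inflates the count. The second lowers it if the patient is not counted. Section 14 states that no separate SAP will be issued, so no later document will settle the schedule.

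New therapy is a related gap. Section 5.3 ends assessments when it starts, footnotes f and x keep these patients in Active Follow-Up, and Section 14.1.2.2 censors them at the last assessment before it. That censoring serves time-to-event PFS; the PFS-6 proportion has no matching rule.

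**Working it through.** **1. The texts side by side.** Take a patient who stops at month 3 without progression. Footnote x and Active Follow-Up require no particular interval. Section 14.1.2.2 requires a scan every 8 weeks until progression. The Treatment Phase text gives the same result, because the later of progression and discontinuation is progression, although it sits under a treatment heading. Sections 11 and 11.2 conflict only by making no exception for patients off treatment. The direct conflict therefore rests on three statements.

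**2. The plan's own figures.** Inputs: n = 25, success at 10 or more, p0 = 0.26, p1 = 0.51 (Section 14.1.4); stop at 2 or fewer of 10 (Section 14.1.5.1).
- Single stage, P(X >= 10 | 25, p): 0.0893 at 0.26 and 0.9036 at 0.51, matching the stated 0.089 and 90%.
- Interim stop, P(X <= 2 | 10, p): 0.496 and 0.048, matching the stated 0.5 and 0.048.
- With the interim included, pass(p) = sum over k = 3..10 of P(X1 = k | 10, p) x P(X2 >= 10 - k | 15, p). This gives 0.082 at 0.26 and 0.880 at 0.51, the baseline used below.

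**3. Missed progression.** The early-stop share (among patients still progression-free), the missed share and the stop month are assumptions. With a constant hazard, h = -ln(0.26)/6 = 0.2245 per month, so S(2) = 0.638, S(4) = 0.407 and S(6) = 0.26. The apparent rate for a stop at month t is p = 0.26 + share x missed x (S(t) - S(6)).

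| Share / missed | Stop at month 4: p, pass | Stop at month 2: p, pass |
|---|---|---|
| 10% / 25% | 0.2637, 0.089 | 0.2695, 0.101 |
| 10% / 50% | 0.2674, 0.096 | 0.2789, 0.121 |
| 20% / 50% | 0.2747, 0.112 | 0.2978, 0.170 |

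Only the product of the two shares matters, so 20% / 25% equals the second row. Expected early stoppers are 25 x share x S(t): 1.0 (month 4) or 1.6 (month 2) at 10%, and 2.0 or 3.2 at 20%. The pass probability reaches the 0.10 limit at p = 0.2692. That corresponds to share x missed = 0.0092 / (S(t) - S(6)), or 0.062 for month 4 and 0.024 for month 2.

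**4. Unknown status.** If unknowns are unrelated to outcome and not counted as progression-free, one among 25 gives a false-positive probability of 0.064 and power 0.842; two give 0.048 and 0.794. One unknown among the first 10, not counted, moves the interim stop probability to P(X <= 2 | 9, p): 0.573 at 26% and 0.080 at 51%.

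**5. The scan grid and the landmark.** Scans fall at weeks 8, 16, 24 and 32 (+/- 1), and six months is about week 26. Week 24, at latest week 25, precedes the landmark; week 32 is the first scheduled scan after it. If only progression up to week 24 is seen in time, the same hazard gives p = 0.26^(24/26) = 0.288 and pass probability 0.144.

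**The case against.** The strongest reply is that the documents do not direct fewer scans. Both calendars mark imaging at the End of Treatment and Active Follow-Up visits, and Sections 5.3 and 11 allow extra scans. Clinical deterioration also counts as progression (Table 11.2-1). Cohort 2 patients who stop only ipilimumab may continue nivolumab (Sections 6 and 6.4) and so stay on the 8-weekly schedule. This stands: the group is probably small, and every share in the table is assumed.

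A second reply is that the 8-week grid is itself coarse. The 0.144 in step 5 applies to patients on schedule and exceeds five of the six values in the table. This also stands. The table measures the change from a baseline in which every progression by month 6 is seen by then, which the schedule does not achieve even on treatment.

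A reader might infer that late detection can only push a patient toward success. The documents do not support that. Sparse scanning can also leave status unknown, and if such patients are not counted, power falls (step 4).

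A reader might also infer that the interim rule is unworkable because *evaluable* is not defined for PFS-6. Section 14.1.5.1 times the interim by ten patients followed for at least six months, and Section 14.2 makes treated participants the efficacy set. Together they give a usable reading. It cannot mean response-evaluable, since Section 11.5 keeps patients with non-measurable disease in the PFS analysis.

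**Conclusion.** The inconsistency is real and touches the primary count. No stated design figure is shown to be wrong. Under the assumed shares the two-stage false-positive probability moves from 0.082 to between 0.089 and 0.170; for a stop at month 4 with a product of shares of 0.05 or less it stays under 0.10. These values rest on a constant hazard, the assumed shares and stop months, and missed patients being counted as successes.

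The claim that five passages contradict the calendar goes too far: three do so directly, and two merely lack an exception. The *evaluable* point is a clarification.

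Separately, one rule for secondary PFS is wrong as written. Section 14.1.2.2 censors living patients with no on-study tumor assessment at last follow-up, so time in which nobody looked counts as progression-free.

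**What to change.** 1. Reconcile Section 5.3 (Active Follow-Up) and footnotes f and x with Section 5.3 (Treatment Phase) and Section 14.1.2.2. Non-progressed patients, on or off treatment, keep the 8-weekly (+/- 1 week) assessment through the first scheduled scan at or after six months, which is week 32, with discretion only afterwards. This aligns off-treatment with on-treatment patients; it does not remove the coarseness of the grid. Section 14 should therefore say how progression first seen at week 32 counts, since the dating rule would place it after six months.
2. State that a patient who starts new anti-cancer therapy before month 6 without progression is not counted toward the 10 of 25, and make Section 5.3 and the footnotes agree on assessments after that point.
3. As a clarification, read *evaluable* in Section 14.1.5.1 as treated and followed six months, with earlier progression or death counted as an outcome.
4. Label any counting rule applied to Cohort 1 as set after its outcomes were described (Section 2.4).
5. For secondary PFS, censor living patients with no on-study assessment at day 1.

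**Cost.** The scan change acts mainly on Cohort 2, which opens after Cohort 1 enrolment is complete (Section 1). A stop at month 4 leaves scans at weeks 24 and 32; a stop at month 2 adds week 16. At the 26% rate and the assumed shares that is at most about 2 (1.0 x 2) to 10 (3.2 x 3) scans per cohort, all already required by Section 14.1.2.2. Item 2 costs some power: one such patient, unrelated to outcome, lowers it from 0.880 to 0.842.

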### 10.3 Safety Assessments

At baseline, a medical history will be obtained to capture relevant underlying conditions. The baseline examinations should include weight, height, Karnofsky Performance Status, BP, HR, temperature, 12-lead ECG and oxygen saturation by pulse oximetry at rest and after exertion and should be performed as noted in the Study Calendars. Baseline signs and symptoms are those that are assessed within 14 days prior to registration. Concomitant medications will be collected from within 28 days prior to registration through the study treatment period.

Baseline local laboratory assessments should be done within 14 days prior to registration include: CBC w/differential, ANC, platelets, Hgb; Chemistry panel including ALT, AST, total bilirubin, alkaline phosphatase), BUN or serum urea level, creatinine, Ca, Mg, Na, K, Cl, LDH, glucose, amylase, lipase, TSH, total T4, and Hep B and C testing (HBV sAg, HCV Ab or HCV RNA) (see Table 6.1-1). Serum pregnancy testing for WOCBP (done locally) must be performed within 72 hours prior to the initial administration of study drug at baseline. Where required by local regulations, an HIV test must also be performed.

Subjects will be evaluated for safety if they have received any study drug. Toxicity assessments will be continuous during the treatment phase. During the on-study phase, toxicity assessments should be done in person. Once participants reach the survival follow-up phase, either in person or documented telephone calls to assess the participant's status are acceptable.

Adverse events and laboratory values will be graded according to the NCI-CTCAE version 4.0. Adverse events experienced by participants will be collected and recorded from the first dose of study treatment up to the 30-Day Post Drug Visit of the last dose of study medication (+/- 7 days depending on when 30-Day Post Drug visit/contact occurs) and all SAEs (related and unrelated to trial treatment) up to 100 days after the last dose of trial treatment or the start of new anti-cancer treatment, whichever comes first. Afterwards, report only SAEs that are considered related to trial treatment.

On-study weight, Karnofsky performance status, and vital signs should be assessed at each on-study visit prior to dosing. Vital signs should also be taken as per institutional standard of care prior to, during and after dosing. The start and stop time of the nivolumab infusion administration should be documented. Physical examinations are to be performed as clinically indicated. If there are any new or worsening clinically significant changes since the last exam, report changes on the appropriate non-serious or serious adverse events page.

Additional measures, including non-study required laboratory tests, should be performed as clinically indicated or to comply with local regulations. On-treatment 12-lead ECGs should be obtained if clinically indicated. Laboratory toxicities (e.g., suspected drug induced liver enzyme elevations) will be monitored during the follow-up phase via on site/local labs until all study drug related toxicities resolve, return to baseline or are deemed irreversible.

Oxygen saturation by pulse oximetry should be obtained prior to each dose of nivolumab and at any time a participant has any new or worsening respiratory symptoms. (If screening pulse oximetry at rest and after exertion performed within 3 days prior to first dose, does not need to be repeated prior to C1D1 dose). A reading at rest should be obtained at each time point. If a participant shows changes on pulse oximetry or other pulmonary related signs (e.g., hypoxia, fever) or symptoms (e.g., dyspnea, cough) consistent with possible pulmonary adverse events, the participant should be immediately evaluated to rule out pulmonary toxicity. An algorithm for the management of suspected pulmonary toxicity can be found in the Appendix B.

CONFIDENTIAL

This document is confidential. Do not disclose or use except as authorized.

Some of the previously referred to assessments may not be captured as data in the eCRF. They are intended to be used as safety monitoring by the treating physician. Additional testing or assessments may be performed as clinically necessary or where required by institutional or local regulations.

